#### 5.3 Gestational age (GA) at maternal infection

In a full data analysis, the target parameter here is not a single date, but a *probability distribution* for each woman, representing when the onset of infection was likely to have occurred, relative to the date of conception which may itself be imperfectly known. To simplify presentation in this SAP we represent this as a discrete distribution in units of one week. Information on the distribution of GA at infection will be derived from one or more of the following

- (a) the date of symptoms, if reported
- (b) dates of a first PCR+ test result and subsequent PCR results
- (c) seroconversion, between last IgG- and first subsequent IgG+
- (d) dates of a first IgM+ and subsequent IgM tests
- (e) dates of an initial IgG+ followed by a rising IgG titer subsequent IgG tests
- (f) avidity tests may also be used to help estimate date of infection, especially in samples that are IgM+ and/or IgG+ at recruitment

Note that an initial PCR+ or IgM+ test result is only informative about timing of infection to the extent that the population distributions of PCR persistence and IgM persistence are known. Thus, test persistence information will be critical in estimating GA at maternal infection (see *Section 7.4*).

In practice, if the tests all had perfect sensitivity and specificity, the sequence of test results would either indicate no maternal infection during pregnancy, or it would define an *interval* during which infection has occurred. The persistence distributions, if relevant, will impact on the probability distribution of GA at infection *within* that interval. The issue of test accuracy adds a further layer of complexity, discussed in the next section.

A third source of information is the weekly local surveillance of incident cases of confirmed or suspected ZIKV, DENV and CHIKV [4]. If we reasonably assume that the attack rates in the general population are proportional to attack rates in the pregnant women being recruited, the surveillance data represents an *a priori* distribution of GA at maternal infection within the interval defined by the sequence of tests. The PCR or IgM persistence distributions, if relevant, will combine with the surveillance information to define maternal GA at infection.

Author: [name] (UNIVBRIS)

16

#### 5.4 Taking test sensitivity, specificity and cross-reactivity into account

PCR tests can be regarded as effectively 100% specific, but they have a short detection window, which varies between individuals. We refer to this as the test's persistence distribution. Serological tests vary in their specificity and sensitivity. Failures of specificity (false positives) can arise for several reasons. While some may be due to a random signal that has exceeded the test's threshold, other false positives may be due to cross-reaction to antibodies to related viruses. Currently available DENV and ZIKV IgM tests react to each other's IgM, and to other flavivirus IgM. We can therefore anticipate that ZIKV and DENV IgM test specificity might vary between collaborating centers, reflecting the geographical distribution of other viruses to which they are cross-reactive. In addition, although IgM antibody is usually assumed to persist for 12 weeks, in some individuals it may persist for many months. Therefore, if IgM is due to an infection acquired many months before the pregnancy, we might regard it as an *analytic* true positive, but a *diagnostic* false positive.

Information on the effective sensitivity and specificity of IgG and IgM assays in different centers is currently incomplete, but will be systematically developed under the ZIKA-VID program. Sources of data on properties of diagnostic tests, for use in ZIKA-VT data analyses, will be updated regularly (see *Appendices 3 & 4*).

Reliable estimates of the sensitivity and specificity of each individual test are not, by themselves, enough to determine the probability that a woman has experienced an infection in pregnancy given her test results. Each woman will be tested on multiple occasions, and on multiple tests. Interpretation of these sequences of tests is complex as we can anticipate there are strong correlations, conditional on true infection status, both between tests results at the same time, and between tests of the same type over time. Rules for determining whether a sequence of tests and clinical findings should be considered as a reflecting a "confirmed", "definite" or "possible" maternal infection will be drawn up by the Expert Diagnostics Group (*Appendix 1*).

In order to use information on test sensitivity and specificity, we must also take into account the *absolute* risk of infection in each pregnant woman during the period when she is pregnant. A ZIKV IgM+ result is more likely to be a false positive if there are few surveillance reports of ZIKV at that time; and more likely to be a DENV infection if large numbers of DENV are being reported. Estimates of the *temporal trends* in infection of ZIKV, DENV and CHIKV are available from routine surveillance sources, as noted above; to obtain estimates of the absolute risk surveillance data must be supplemented by data on the proportion of infections, whether symptomatic or not, that are reported to the surveillance center. This proportion, which will vary between ZIKV, DENV and CHIKV, can be *approximately* estimated by aligning weekly surveillance reports with data from ZIKA-VT (See *Section 8.1*).

Following reports of sexual transmission of ZIKV, ZIKA-VT will be collecting information on infection in fathers / partners. We will explore the possibility of using this information alongside surveillance data when estimating the likely timing of maternal infection.

Author: [name] (UNIVBRIS)

**17** 

# 6. Vertical transmission risk and outcomes: basic statistical outputs

Basic analyses, without attempts to correct for sensitivity, specificity and cross-reactivity, and making only the simplest assumptions about test persistence, are set out as a series of table shells. The most likely trimester of maternal infection in these tables would be derived from rules based on dates of tests and assumptions about test persistence.

Table 1 provides crude estimates of the risk of vertical transmission and the risk of congenital anomalies, by most likely trimester of presumed maternal infection, and by symptoms.

Table 2 provides a simple listing of congenital anomalies.

Table 3 is a breakdown of outcomes of pregnancy (fetal death, stillbirth) by indicators of maternal infection in pregnancy.

Table 4 represents a generic form of analysis for delivery data and subsequent pediatric outcomes, separate for ZIKV, DENV, and CHIKV, and by trimester of infection, and laid out by birth cohort (Vertically infected, Maternal Infection but no vertical infection, No maternal infection). Covariates can be taken into account by multiple regression.

With so many outcomes to examine, in three distinct diseases, the Table 3 and Table 4 analyses must be considered as hypothesis-forming, not hypothesis-testing.

Tables 1-4 will be computed with standard software, such as SAS, STATA, or R. However, as pointed out in Section 5, any analyses involving the denominator for vertical infection, so especially Table 1 estimates, will be vulnerable to very considerable biases due to inaccuracy in identifying the timing of maternal infection, and indeed, whether there was a maternal infection during pregnancy at all.

The methods set out in the next section are designed to solve these problems, leading to gestational age at infection being represented as *probabilities* that infection occurred in the 1st, 2nd, and 3rd trimester, rather than the usual 0,1 "dummy covariates" used in conventional analyses of gestational age as a risk factor.

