#### 5.2 Numerator for VTR

Fetuses will be regarded as vertically infected if fetal or placental tissue, or amniotic fluid, tests PCR+. Children will be regarded as vertically infected on the basis of IgM or PCR evidence within 7 days of delivery. Infants who lose antibody will be regarded as not vertically infected: this includes infants in whom a falling IgG titer is observed as well as those who become IgG-.

There are reports of children with clinical signs of congenital infection, such as microcephaly, whose mothers were infected in pregnancy, but in whom no laboratory evidence of congenital ZIKV can be obtained from testing serum and CSF for IgM and PCR. Definitions of congenital zika in the absence of laboratory evidence are being developed [2, 3], which may be revised as new data becomes available. Although the evidence is not clear at the time of writing, it seems likely that these infected children will remain IgG antibody positive.

Infants who are IgG antibody positive when last seen may be congenitally infected. The probability that they are congenitally infected depends on two factors: firstly, their age, because maternal antibody declines over time and is usually absent within 15 months. Secondly, the risk of post-natal

Author: [name] (UNIVBRIS)

15

infection. Appendix 5 describes statistical analyses that use data on antibody loss in control children born to IgG+ mothers, and data on post-natal infection on initially IgG- newborns, to estimate the probability of vertical infection in all IgG+ infants whose infection status cannot otherwise be determined.

It remains possible either that congenital infection can take place, causing damage, and clearing prior to delivery and leaving no laboratory markers; or that maternal infection affects fetal development without crossing the placenta. It is for this reason that ZIKA-VT includes a 2nd control group, of children born to mothers with no infection in pregnancy.

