#### **TABLES**

#### Table 1: Risks of Vertical Transmission and Congenital malformation.

#### **Definitions:**

- 1. Presumed maternal infection based on PCR+, IgM+, Seroconversion or rising IgG titer
- 2. Trimester, most likely trimester based on test dates and persistence
- 3. Vertical infection based on IgM+, PCR+ in cord or sample from newborn < 7days old, or persistent antibody.
- 4. Severe and mild congenital malformation, to be defined

	Trimester of presumed infection	Symptoms during pregnancy	Number of Mothers infected	Number Vertically infected	Number of Congenital malformations (severe)	Number of Congenital malformations (mild)
	1	Yes				
		No				
ZIKV	2	Yes				
		No				
	3	Yes				
		No				
	1	Yes				
		No				
DENV	2	Yes				
		No				
	3	Yes				
		No				
	1	Yes				
		No				
CHIKV	2	Yes				
		No				
	3	Yes				
		No				

Author: [name] (UNIVBRIS)

34

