## Table 2. Listing of all congenital anomalies at delivery

#### Including:

Most likely trimester of maternal infection
Ultrasound findings
Outcome of pregnancy: fetal death, stillbirth, livebirth
Gestational age at delivery (GA)
Birthweight, birthweight for GA, head circumference, head circumference for GA.
Description of anomalies at delivery: cranial morphology; brain anomalies; congenital contractures; neurological sequelae.

Author: [name] (UNIVBRIS)

Table 3. Outcomes of pregnancy: generic summary tables and covariate analyses

- Individed	- .	1		T					
	Trimester	Symptoms	Number of						
	of	during	Mothers in						
	presumed	pregnancy	category						
	infection	,,							
	1	Yes							
Monthoul		No		Outcomes of pregnancy to be					
Vertical	2	Yes		tabulated.					
infection		No		-					
ZIKV	3	Yes							
		No		Abnormal ultrasound findings					
	1	Yes		Abnormal ultrasound findings:					
Vertical		No		specific abnormalities, groups of					
Infection	2	Yes		abnormalities, etc. to be tabulated					
DENV		No		Fetal deaths (1 st and 2 nd trimester)					
	3	Yes		Fetal deaths (3 rd trimester)					
		No		Livebirths					
	1	Yes							
		No		Covariates to be considered for					
Vertical	2	Yes		regression analysis Centre					
Infection		No							
CHIKV	3	Yes		Year - season					
		No		Co-infections in the mother					
Maternal	1	Yes							
infection		No		Previous infection in mother, same or					
NO vertical	2	Yes		different arbovirus					
infection		No		Maternal age					
ZIKV	3	Yes		Obstetric history (e.g. previous stillbirth,					
		No		congenital abnormalities)					
Maternal	1	Yes		Comorbidities (e.g. sickle cell, diabetes)					
infection	_	No		Smoking /alcohol /drug use					
NO vertical	2	Yes		SES markers					
infection	_	No							
DENV	3	Yes							
	3	No							
Maternal	1	Yes							
infection	_	163							
NO vertical		No		1					
infection		140							
CHIKV	2	Yes		1					
J	_	No		1					
	3	Yes		1					
	3			1					
		No	1						

Author: [name] (UNIVBRIS)

Table 4. Outcomes by birth cohort: generic summary tables and covariate analyses

	Trimester of	Symptoms during	Number of Mothers	Outcome	Outcomes to be tabulated:
	presumed infection	pregnancy	in category		Number (%) preterm <37 completed weeks
	1	Yes			Gestational age (mean, sd)
		No			Number (%) livebirths
Vertical	2	Yes			Number (%) neonatal deaths
infection		No			Number (%) deaths at one year
ZIKV	3	Yes			Birthweight (mean, sd)

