## APPENDIX 5. Role of Antibody persistence in diagnosis of congenital infection

The criteria for congenital infection (CI) are: PCR+ in serum, urine or CSF OR IgM+ in serum, urine or CSF; OR congenital zika syndrome meeting an agreed definition (see *Section 5.2*) Infants who lose IgG antibody, or who have consistently falling IgG titers, will be regarded as not CI.

The remaining children are those that remain IgG+ at last follow up. They have a probability of being congenitally infected that increases with time, but it is necessary to take into account that they may have acquired antibody following a post-natal infection.

Suppose we have available information on the probability Ab(t) that an uninfected child born to an antibody +ve mother remains IgG+ t weeks after delivery. Suppose also that we have information on the probability Pn(t) that an initially IgG- newborn is IgG+ t weeks after birth as a result of a postnatal infection.

Now consider the babies born to women infected in pregnancy: all will be initially lgG+. The proportion lgG+ at time t is:

$$X(t) = (V + (1-V)Ab(t)) + (1-V-(1-V)Ab(t))Pn(t)$$

If there was no post-natal acquisition of antibody, we should observe X(t) fall off to an asymptote V representing the vertical transmission rate. Instead we expect X(t) to fall until all maternal antibody is lost, and then continue to rise in response to postnatal acquisition. As we can observe Ab(t) and X(t), and we have data on and Pn(t), we can recover an estimate of V.

If AB(t) indicates having IgG antibody at time t, then the probability that a child who is IgG+ at age t is CI is:

$$p(CI \mid AB(t)) = \frac{p(AB(t) \mid CI).p(CI)}{p(AB(t) \mid CI).p(CI) + p(AB(t) \mid \overline{CI}).p(\overline{CI})}$$
$$= \frac{V}{V + (1 - Ab(t))V}$$

These analyses can be extended to include covariates, and can be integrated into the calculation of the vertical transmission rate (Section 7.1) [14].

Data on Ab(t) will be generated from within ZIKA-VT, but we will also refer to other sources of information as listed in the following table, which will be updated regularly:

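### Table 4 compares early deaths and one-year outcomes across infant cohorts whose membership depends partly on serology that only survivors can supply

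*SAP*

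**What the plan says.** Section 6 describes Table 4 as "laid out by birth cohort (Vertically infected, Maternal Infection but no vertical infection, No maternal infection". Among the outcomes listed for every row are neonatal deaths, "Number (%) deaths at one year" and severe clinical outcomes at 1 year. The shell has no row for infants of undetermined status.

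The rules that sort the infants of infected mothers are these:

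- **Infected, early route (Section 5.2):** "Children will be regarded as vertically infected on the basis of IgM or PCR evidence within 7 days of delivery".
- **Infected, late route (Table 1, definition 3):** "Vertical infection based on IgM+, PCR+ in cord or sample from newborn < 7days old, or persistent antibody".
- **Not infected (Section 5.2):** "Infants who lose antibody will be regarded as not vertically infected: this includes infants in whom a falling IgG titer is observed".
- **Not infected (Appendix 5):** "Infants who lose IgG antibody, or who have consistently falling IgG titers, will be regarded as not CI".

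Section 5.2 adds that an IgG-positive infant's age at last test matters "because maternal antibody declines over time and is usually absent within 15 months". Infants who meet none of these rules are to receive a probability of infection (Section 5.2, Section 10.2 item 1, Appendix 5). Section 7.7 describes what passes from the full model into Tables 3 and 4, and names only probabilities for the timing of the mother's infection.

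**The concern.** First-week PCR or IgM can put an infant in the vertically infected (VI) row straight away. The only stated evidence for the row of maternal infection without vertical infection (no-VI) is a change in IgG, which requires the infant to be alive and retested. Appendix 5 treats all infants of mothers infected in pregnancy as IgG+ at birth, so a PCR-/IgM- infant who dies at ten days is undetermined on the plan's own terms. The persistent-antibody route into VI also requires survival, to beyond the loss of maternal antibody.

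Table 4 therefore compares mortality between groups in which part of the membership is conditional on having survived. The contrast serves Section 2.1, which asks for outcomes of maternal infection (i) with and (ii) without in utero transmission. An artefact here affects VI against no-VI, and also no-VI against the cohort with no maternal infection, for whom no antibody has to resolve.

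**Working it through.** The plan gives no figure to reproduce, nor any value for infant mortality, the vertical transmission rate, the age at which a titer fall is first seen, or the share of VI found only by antibody. All inputs below are assumptions. True mortality is set equal in VI and no-VI, so an unbiased table shows a ratio of 1.

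**Inputs:** one-year mortality q = 2% or 4%, half of it neonatal (first month) and the rest spread evenly over the next 11 months; c = age in months at which IgG loss or fall is first documented; f = share of VI found only by persistent antibody, after 12 months; V = transmission rate, 5% to 30%.

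**Reading A: infants who die before resolution are left out of no-VI.** Deaths before age c: D(c) = q/2 + (q/2)(c − 1)/11. No-VI one-year mortality: (q − D(c))/(1 − D(c)). With q = 4% and f = 0, VI mortality is 4.00%:

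| c | D(c) | no-VI mortality | VI : no-VI |
|---|---|---|---|
| 1 month | 2.00% | 2.04% | 1.96 |
| 3 months | 2.36% | 1.68% | 2.39 |
| 6 months | 2.91% | 1.12% | 3.56 |
| 12 months or later | 4.00% | 0 | unbounded |

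At q = 2% the first three ratios are 1.98, 2.42 and 3.61.

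If some VI is found only by antibody, VI mortality becomes (1 − f)q/[(1 − f) + f(1 − q)]. For f = 50% this is 0.020/0.980 = 2.04%, and the ratio at c = 3 months is 2.04/1.68 = 1.2. It is 1.8 at f = 25% and 0.6 at f = 75%.

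**Reading B: no-VI is everyone exposed who does not meet a VI criterion.** Infants whose infection would have been found only by antibody, but who die first, now count in no-VI. VI mortality is as in the last formula; no-VI mortality is [(1 − V)q + Vfq]/[(1 − V) + Vfq]. With q = 4% and V = 10%:

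| f | VI | no-VI | VI : no-VI |
|---|---|---|---|
| 0 | 4.00% | 4.00% | 1.00 |
| 25% | 3.03% | 4.11% | 0.74 |
| 50% | 2.04% | 4.21% | 0.48 |

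Over V = 5% to 30% and both values of q, the ratio is 0.68 to 0.75 at f = 25% and 0.42 to 0.50 at f = 50%.

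**First-week assignment.** If every exposed infant is classed by first-week tests alone, both groups have mortality q and the ratio is 1.00.

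**Would the Appendix 5 probability repair the table?** Not as printed. V/[V + (1 − Ab)V] simplifies to 1/(2 − Ab), where Ab is the probability that an uninfected child is still IgG+. At Ab = 1, the situation at an early death, it gives 1 for any V. As Ab falls to 0 it drops to 0.5, although the appendix says the probability rises with time. Ignoring postnatal infection, Bayes' rule gives V/[V + (1 − V)Ab], which runs from V at Ab = 1 up to 1 at Ab = 0.

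Take q = 4% and suppose all deaths are undetermined and survivors correctly classed. The printed formula then gives VI mortality of q/[V(1 − q) + q] = 0.040/(0.096 + 0.040) = 29% at V = 10% (45% at V = 5%, 12% at V = 30%), against 0% in no-VI. The Bayes weight gives 4.0% in both.

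**The case against.** The strongest reply is that the antibody-loss rule is sufficient, not necessary. Section 5.2 does not say that only infants who lose antibody enter no-VI, and nowhere does the SAP say that undetermined deaths are dropped. Table 1 defines only the positive state, Section 3.1 names three birth cohorts with no undetermined group, and Section 7.1 codes infection as 0 or 1, so no-VI may be meant as the complement. This stands as far as it goes. A reader might infer that neonatal deaths in no-VI are zero by construction and that VI must look more lethal; the documents do not support either. Even on Reading A, a falling titer is enough, so deaths after it is seen are kept, and zero neonatal deaths requires that no fall be documented in the first month.

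The complement reading does not rescue the table, however. It exchanges one survival condition for another and biases the ratio the other way (Reading B).

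Three further replies carry some weight. Section 10.2 gives undetermined children a probability, but Section 7.7 does not carry it into Table 4 and the printed formula misallocates early deaths. Section 10.2 item 4 covers censoring and extreme-case analyses for loss to follow-up, which is a different problem from cohort entry that depends on survival. Section 5 makes the expert group responsible for the criteria for vertical transmission, so it could settle the matter, but this document does not. The clinical-syndrome criterion in Appendix 5 can class some affected infants without later serology, which narrows the gap without closing it.

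Finally, Section 6 calls Table 4 hypothesis-forming, and the mortality contrast is not one of the two pre-specified outcomes in Section 10.4. That limits the consequence but does not remove the artefact.

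**Conclusion.** The concern holds in this form: the plan does not fix the cohort of exposed, PCR-/IgM- infants who die before serological resolution, and both natural readings make the Table 4 comparisons of early outcomes conditional on survival. With equal true mortality, the apparent one-year VI : no-VI ratio is about 2.4 or 3.6 if these infants are left out and a titer fall is first seen at 3 or 6 months with all VI found at birth. It is about 0.7 or 0.4 to 0.5 if no-VI is the residual group and 25% or 50% of VI is found only by antibody. Mixed cases fall between.

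The direction is therefore not established. Much larger ratios can be produced: with 75% of deaths neonatal, the rest spread evenly over weeks 4 to 52, and classification at week 39, only 0.25 × (52 − 39)/48 ≈ 7% of no-VI deaths are kept, a ratio near 15. That needs the strict reading, no VI found by antibody, and figures that the SAP does not give, so it should not be cited as the size of the bias. The point merits correction because the table answers a stated objective, but it does not touch the analysis of the vertical transmission rate itself.

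**What to change.** - For Table 4 outcomes that can occur before serology resolves (delivery outcomes, neonatal and one-year deaths, severe outcomes at 1 year), assign exposed infants by PCR/IgM evidence within 7 days, positive or negative.
- Use antibody-based classification only for outcomes measured after it, with follow-up starting at the age of classification, and show an undetermined row.
- Allow weighting by the probability of congenital infection only after the Appendix 5 formula is corrected; ignoring postnatal infection it should be V/[V + (1 − V)Ab(t)].

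The cost is SAP wording and a table shell, with no new data. The drawback is that infected infants detectable only by antibody sit in the first-week-negative row for early outcomes. This dilutes the contrast by an amount that the documents do not allow to be quantified.
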